1.7 Determination of Sample Size

The sample size required for the MOVE Trial was determined via simulation based on the available WBCT HO volumes from the NHS and the observed efficacy of palovarotene treatment in Phase 2. The NHS will serve as the external control group with, for the purposes of the determination of sample size, the assumption that 45 subjects will have baseline, 1-year, and 1.5-year WBCT HO volumes and 45 subjects will have baseline, 1-year, and 2-year WBCT HO volumes. It is also assumed that approximately 50% of these 90 subjects will enter the Phase 3 study to begin palovarotene treatment.

There are three interim efficacy analyses – with futility analyses at the second and third interim analyses – and a final analysis planned. Assuming a one-sided, overall type I error rate of 2.5%, the Lan-DeMets alpha-spending function with O’Brien-Fleming parameterization was used to determine stopping boundaries (see [Section 0](#) for additional details).

Available pairs of NHS WBCT scans for 65 subjects taken one year apart and read using the original NHS single-reader process were used to tabulate the number of body regions with new HO and the mean and standard deviation (SD) of new HO volume in each body region ([Table 1](#)). The original 15 body regions from the NHS WBCT scans were mapped to approximate the 9 body regions that will be used in the MOVE Trial. The mean (SD) number of body regions with new HO per subject in approximately one year was 0.707 (1.11), i.e., there were 46 body regions with new HO in 65 subjects.

Table 1. NHS WBCT Scan Results by Body Region

Body region	Number of observations	Number of regions with new NO	Proportion of regions with new HO	Volume change given new HO in region (in thousands mm ³)	
				Mean	SD
Neck, upper spine and chest	64	12	0.19	25.83	21.06
Shoulder (left, right)	130	7	0.05	4.69	3.08
Elbow, hand and wrist (left, right)	125	1	0.01	31.27	-
Lower spine and abdomen	65	11	0.17	16.22	19.24
Hip (left, right)	130	9	0.07	81.17	89.65
Knee and distal lower extremity (left, right)	128	6	0.05	9.04	14.64

Simulations to assess power were conducted as follows:

1. A subject-level rate of body regions with new HO were randomly drawn from a gamma distribution with mean = 0.707 and SD = 1.11.

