1.10 Statistical Modifications to the Statistical Analysis Plan

1.10.1 Statistical Modifications to the Statistical Analysis Plan, V1.0

The primary and secondary efficacy analyses described in Protocol Amendment 1 do not include explanatory covariates. Because recent studies – Clementia’s NHS as well as other studies – suggest that age may be important for flare-up rate and the formation of new HO, age (<18, ≥18 years) and additional categorical variable sex (Male, Female) is included in the primary and secondary efficacy analyses.

The analysis of the secondary endpoints proportion of subjects with any new HO and number of body regions with new HO will both be conducted using the Bayesian compound Poisson model used in the primary efficacy analysis; in fact, the inference is identical for these two secondary endpoints. Within the compound Poisson model, $\theta_{1,1} < 1$ implies both a lower proportion of subjects with any new HO and a smaller number of body regions with new HO for palovarotene-treated subjects.

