The primary efficacy endpoint is the annualized change in new HO volume (as assessed by WBCT). The change in new HO volume is calculated by summing the increase in HO volume across all body regions for which new HO has occurred where the increase in HO volume per region is defined as the square-root of the volumetric increase in that region. The square-root transformation is used to reduce the influence of outliers. Transformation of volumetric changes has been used in related contexts. For example, a log transformation has been used to model volumetric increases in the kidneys of subjects with autosomal dominant polycystic kidney disease^{1,2}. The change in new HO volume is modeled using a Bayesian compound Poisson distribution. The Bayesian compound Poisson distribution assumes that the change in new HO volume can be modeled as a compound distribution of the number of body regions with new HO, K , and the new HO volume per region where new HO has occurred, Z . The number of body regions with new HO in subject i for WBCT scan j with duration w_{ij} (the time between scan j and the previous scan) is distributed as

$$K_{ij} \sim \text{Pois}(\lambda_{i,j} * w_{ij} * \theta_{1,t(ij)});$$
$$\log(\lambda_{i,j}) = \log(\lambda_i) + \beta_1 X_{1,i} + \beta_2 X_{2,i,j}$$

The subject-level rate λ_i follows a gamma distribution and accounts for potential correlation in measurements from the same subject; $t(ij)$ is an indicator function equal to 1 if the subject was on treatment at the time of the j th WBCT scan and 0 if the subject was not on treatment. Therefore, the marginal distribution of the number of body regions with new HO follows a negative binomial distribution, which requires much less restrictive assumptions than a Poisson distribution and does not tend to result in an underestimate of the variance.

Letting $\theta_{1,0} = 1$, the variable $\theta_{1,1}$ is the multiplicative effect of palovarotene treatment on the rate of body regions with new HO. Covariates are included in the analysis of the number of body regions with new HO to adjust for potential explained differences in the rate of new HO based on the subject's sex, $X_{1,i}$, and age at time of scan, $X_{2,i,j}$. Age at the time of scan is represented as a factor variable with 0 for <18 years old and 1 for ≥ 18 years old. Covariate effects $\exp(\beta_1)$ and $\exp(\beta_2)$ are multiplicative effects of sex and age on the rate of body regions with new HO.

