A subject-level random effect will be used to account for the correlation among repeated measures on the same subject as subjects may contribute follow-up from both the NHS and the current study. Baseline HO volume divided by age will be the only covariate included in the model, in addition to the factor identifying study of origin. The LME model will be fitted using only a subject's observations associated with the longest follow-up in the NHS and the current study with weights used to account for the different lengths of observed subject follow-up. Missing at random will be assumed for the primary analysis and no imputation of missing data performed.

The wLME analyses will be run using SAS 9.4 or higher. The code will use the following structure:

```
proc mixed data=data;
    class treat usubjid;
    model annrate_newho = treat basetot_bage /s;
    random usubjid;
    lsmeans treat/pdiff=control('0') cl;
    weight fup;
run;
```

In this code, treat is a binary indicator for study (1=MOVE, 0=NHS); usubjid is a unique identifier of subjects (used across all FOP studies); annrate_newho is the annualized rate of new HO; and fup is follow-up in years.

The Bayesian compound Poisson analysis and wLME analysis without square-root transformation and including all assessments on or before December 4, 2019, for subjects <14 years old on the date of their assessment and assessments on or before January 24, 2020, for all other subjects, will be repeated using the Principal PPS after the third interim analysis.

Descriptive statistics summarizing the total HO by study visit, change in HO volume by study visit, and change in HO volume from baseline by study visit will be provided. Tables summarizing annualized new HO will also be produced. Summaries will also be provided by body region. Summaries of new HO coincident with flare-ups and not coincident with flare-ups will also be generated. Summaries of annualized mean New HO, conditional on new HO volume>0 mm³, will be created. HO listings will also be generated.

Missingness, including frequency of WBCT not collected and regions that are not evaluable, will be summarized. Frequency of negative new HO, i.e., apparent reductions in HO overall and by body region (defined below), will also be summarized.

Handling of Reductions in HO

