The following sensitivity analyses will be conducted after the third interim analysis to examine the robustness of the Bayesian compound Poisson analysis without the square-root transformation, unless otherwise specified. All assessments on or before December 4, 2019, for subjects <14 years old on the date of their assessment and assessments on or before January 24, 2020, for all other subjects, will be used. Note that, given the consistency of results between the Bayesian compound Poisson and wLME analyses observed at the second and third interim analyses, the sensitivity analyses below will utilize both methodologies, as described. The results may be summarized jointly in forest plots, as appropriate.

To assess impact of differences between NHS and MOVE:

- Adjustment for additional baseline covariates: This sensitivity analysis will extend the primary efficacy analysis to include additional baseline covariates. These will include baseline HO volume divided by age, age, sex, months since last flare-up, and CAJIS. The palovarotene treatment effect will be estimated using the Bayesian compound Poisson distribution with all covariates included. A similar wLME will also be performed.
- Propensity score analysis: The propensity score, defined as the conditional probability of being treated given the baseline covariates, can be used to balance the baseline covariates across treatment groups.³ Therefore, it can reduce potential bias due to imbalances in the distributions of demographic and disease characteristics between the NHS and MOVE Trial. The propensity scores will be derived from a logistic regression model with the following covariates: baseline HO volume divided by age, age, sex, months since last flare-up, and CAJIS. Each subject's propensity score will be estimated from the logistic regression model, and subjects will be grouped by quartiles of their propensity scores. Propensity score quartile will be used as the only covariate in the Bayesian compound Poisson analysis. wLME will be conducted for each quartile and overall using the 5-level factor as a covariate (in addition to treatment).

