- Restriction to subjects contributing follow-up for both the NHS and MOVE Trial: This analysis will use the wLME analysis method on the subset of the MOVE subjects who transitioned from the NHS and have annualized rates of new HO for both studies. Baseline HO volume divided by age will be the only covariate included in the model, in addition to the factor identifying the study of origin.
- As requested by regulatory agencies, a matched pairs analysis – including subjects who participated in either MOVE or NHS but not both studies – was performed. Caliper-matching used propensity scores described in this SAP. The analysis used a paired t-test.

To assess impact of differences in length of follow-up between NHS and MOVE:

- Analysis restricting subjects to specific durations of follow-up: The WBCT dataset will be restricted to observations associated up to 1-year – interpreted as assessments within the first 15 months of study participation (i.e., midway between Month 12 and Month 18 for MOVE) – and, separately, with up to 2-years of follow-up – interpreted as assessments within the first 27 months of study participation. The analysis method will be wLME.

To assess impact of missing data in MOVE:

- Missing data sensitivity analysis using a tipping point approach: Subjects who discontinue the MOVE study will have volume of new HO imputed using the wLME-modeled treatment effect. The multiple imputations will be scaled to induce 0%, 25%, 50%, 75%, and 100% reductions in the palovarotene treatment effect. The 0% corresponds to subjects who discontinue the MOVE Trial having the same distribution for number of body regions with new HO and change in HO volume per region as the MOVE subjects who did not discontinue; and 100% corresponds to subjects who discontinued the MOVE Trial having the same distributions as the NHS subjects. Missing data will be imputed for the visits in MOVE that were either missed or would have been missed due to study discontinuation prior to December 4, 2019 / January 24, 2020. Analyses in which subjects who discontinue the NHS have volume of new HO imputed may also be considered, while noting that the majority of subjects who discontinued NHS did so to enroll in an interventional study, e.g., MOVE or less frequently, Study PVO-1A-201.

To assess robustness of efficacy signal against choice of wLME as post-hoc analysis:

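### The sensitivity analysis of subjects followed in both the NHS and MOVE is a before-after comparison with no separate age or time term, so any natural trend in new HO, of unstated sign and size, is attributed to palovarotene

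*SAP*

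**What the plan says.** Among the sensitivity analyses meant to assess differences between the NHS and MOVE, SAP 2.4.4 restricts one to people with follow-up in both studies: "This analysis will use the wLME analysis method on the subset of the MOVE subjects who transitioned from the NHS and have annualized rates". Each study must supply such a rate. The covariate rule is "Baseline HO volume divided by age will be the only covariate included in the model, in addition to the factor identifying the study of origin".

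The wLME code given earlier in SAP 2.4.4 agrees. Its fixed part is "model annrate_newho = treat basetot_bage /s", with a random subject effect and follow-up time as the weight. The data rows are the "observations associated with the longest follow-up in the NHS and the current study", so a transition subject supplies one untreated and one treated rate.

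Elsewhere the SAP gives age its own place:

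- SAP 1.10.1 adds age to the primary and secondary models because recent studies "suggest that age may be important for flare-up rate and the formation of new HO".
- In the primary Bayesian model, "Age at the time of scan is represented as a factor variable", split at 18 years.
- For the covariate-adjusted analysis the added baseline covariates are listed as follows: "These will include baseline HO volume divided by age, age, sex, months since last flare-up, and CAJIS". The propensity score uses the same list.

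**The concern.** Nobody moves from MOVE back to the NHS, so the order of the two periods is the same for everyone. Within a person, being treated coincides with being later and older. The model has no term that could separate the two and no untreated group observed over the same passage of time.

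The one covariate cannot do that work. If baseline HO volume divided by age is taken once per subject, it is constant within the person and carries no information about change. If it is taken again at MOVE entry, it is still a ratio of burden to age and not a measure of time elapsed. The SAP does not say which baseline applies here.

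The stake is interpretive. A comparison in which each person is their own control removes stable between-person differences, and agreement with the main result could be taken as independent confirmation. The SAP allows sensitivity results to be shown together in forest plots and places them in the interim study report for the marketing applications (SAP 2.4.4 and 3.3).

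**Working it through.** **Inputs from the documents**

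- Planned follow-up (SAP 2.4.4, Control of Type I Error): 45 NHS subjects for 1.5 years, 45 for 2.0 years, and 80 MOVE subjects for 2.0 years. Check: 45×1.5 + 45×2.0 + 80×2.0 = 67.5 + 90 + 160 = 317.5 years, the SAP's own total.
- Transition subjects (SAP 1.7): "It is also assumed that approximately 50% of these 90 subjects will enter the Phase 3 study to begin palovarotene treatment", so 0.5×90 = 45.
- Data that may enter the endpoint (SAP 2.1.3): MOVE to Month 24, NHS to Month 36.
- Design effect (SAP 1.7): 30% fewer regions and 50% less volume per region, so 1 − 0.70×0.50 = 65%.

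**Assumptions**

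- MOVE follow-up of 1.25 to 2.0 years. The lower value allows for the December 2019 and January 2020 dosing cutoffs and is not stated in the documents.
- MOVE starts when NHS follow-up ends.
- A natural decline d of 5%, 10% or 15% per year. The documents give no value.

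**Gap between period midpoints**

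g = (NHS duration + MOVE duration)/2

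- Shortest: (1.5 + 1.25)/2 = 1.375 years
- Planned longest: (2.0 + 2.0)/2 = 2.0 years
- NHS to Month 36: (3.0 + 2.0)/2 = 2.5 years

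**Apparent reduction from a drug with no effect**

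1 − (1 − d)^g

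| d per year | g = 1.375 | g = 2.0 | g = 2.5 |
|---|---|---|---|
| 5% | 6.8% | 9.8% | 12.0% |
| 10% | 13.5% | 19.0% | 23.2% |
| 15% | 20.0% | 27.8% | 33.4% |

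For example, 1 − 0.90^2.0 = 19.0%. With a natural rise the sign reverses.

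**Does HO volume/age absorb the trend?** The SAP model was simulated with no drug effect: 45 subjects, 400 runs per scenario, and assumed ages uniform over 4-30 or 4-18 years. The covariate was taken at each study's own baseline.

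| Decline, ages | Age-driven change | SAP model estimate | With age at period midpoint added |
|---|---|---|---|
| 10%, 4-30 | −16.7% | −16.5% | −5.0% |
| 10%, 4-18 | −16.9% | −18.3% | −3.1% |
| 15%, 4-30 | −24.4% | −23.8% | −9.4% |
| 15%, 4-18 | −25.1% | −26.5% | −6.8% |

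The covariate absorbs essentially none of the trend. Across both choices of baseline, one-sided false-positive rates (nominal 2.5%) were about 6-8% at a 10% decline and 12-19% at 15%. With no decline at all, re-measuring the covariate at MOVE baseline shifted the estimate by about −5% to −7%; taking it at NHS baseline for both rows gave no material shift. These figures depend on the assumed ages and heterogeneity. With 400 runs, a rate of 2.5% has a standard error of √(0.025×0.975/400) = 0.8 percentage points.

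**The case against.** The case for leaving the plan alone is substantial.

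- **The analysis decides nothing.** SAP 2.4.4 applies no success or futility threshold to any efficacy analysis after the second interim. The two analyses it names as of primary interest use all subjects. This stands.
- **Age is handled elsewhere.** The primary model includes age at scan. The covariate-adjusted and propensity analyses include age as a separate term. The matched-pairs analysis uses those propensity scores and excludes anyone who was in both studies, so it is free of the fixed order. Analyses with different weaknesses can support one another. This stands too, and it confines the point to one analysis.
- **Age is not wholly absent.** It is the denominator of the covariate. A reader might infer that the model ignores age entirely or that treatment is completely confounded with it. Neither is right: age varies between people, so an age coefficient can be estimated. What is aliased is elapsed time within a person.
- **The direction is unknown.** A reader might infer that HO formation falls with age and that the analysis therefore flatters palovarotene. The documents do not say so. SAP 1.10.1 says only that age may matter.
- **The remedies are imperfect.** Within a person, the age difference nearly coincides with treatment, so the coefficient comes mainly from differences between people. Two adjoining annual NHS intervals have midpoints 1 year apart, so an unscaled contrast would remove only 1/2.0 = 50% to 1/1.375 = 73% of a linear trend. SAP 2.4.4 also notes that most people who left the NHS did so to enter an interventional study, so those who stayed may differ.

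None of this supplies the missing time reference in the planned analysis.

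**Conclusion.** The point holds for this one analysis. As specified, it is a before-after comparison that cannot separate palovarotene from the passage of time, and the SAP's own treatment of age elsewhere gives reason to care. The possible bias is about 7-10%, 13-19% or 20-28% for assumed natural declines of 5%, 10% or 15% per year at gaps of about 1.4 to 2.0 years, rising to 12%, 23% or 33% at 2.5 years. It runs against the drug if new HO naturally rises. Sign and size rest entirely on an age trend that the documents do not give.

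A reader might go further and conclude that the primary result is undermined, or that a finding from this analysis could be nothing but ageing. The documents support neither. The primary analysis uses a different model with an age term. To reproduce the 65% design effect by trend alone at a 2.0-year gap would need an annual decline of 1 − 0.35^(1/2.0) = 41%. What follows is narrower: this analysis should not be read as independent confirmation without a time reference beside it.

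**What to change.** Add a supplementary output to this sensitivity analysis:

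1. Refit the wLME with age at the start or midpoint of each period, and describe this as a partial correction.
2. From NHS subjects with at least two annual intervals (scans at baseline and Months 12, 24 and 36), report the later-minus-earlier untreated contrast per year, scaled to each transition subject's NHS-to-MOVE midpoint gap.
3. Report the difference between the MOVE-minus-NHS contrast and that scaled untreated contrast.
4. State whether baseline HO volume divided by age is taken at NHS or MOVE entry.
5. Label the planned estimate as before-after wherever it appears, including any forest plot.

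No new data are needed. The costs are a wider interval, some residual bias after the age term, and possible selection among those who remained in the NHS. SAP 3.3 does not plan to rerun interim-report analyses for the final report, so this would be an addition, and it should be declared post hoc because the sponsor is already unblinded.
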